6.1.3. Part 2 – Repeat Dose, Morning Dose Administration, Days 2-13

	Days 2-13	
	Pre-dose	0h
Study Drug Dose ⁶		X ⁶
Vital Signs (BP, HR, pulse)	X	
12-Lead ECG ¹	X	
Hematology, Chemistry ²	X	
UA ³	X	
Exploratory PD Labs ³	X	
Plasma PK and Metabolite Sampling ⁴	X	
Adverse Event Review	←=====→	
BSFS ⁵	←=====→	
Concomitant Medication Review	←=====→	

- Day 2 (equal to Day 1 24h time point), 7, 12, and 13 only.
- Day 2 (equal to Day 1 24h time point), 4, and Day 7 only
- Day 2 (equal to Day 1 24h time point) and Day 7 only
- Day 2 (equal to Day 1 24h time point), 4, 5, 6, 12, and 13 only
- The number of BSFS stool types will be collected in real time for each 24h period (Section 11.5).
- For cohorts where multiple doses are to be administered either q1h or q16h, Time 0 is the first dose and subsequent doses are per regimen (q1h or q16) and the subsequent doses are not noted on the T&E Table.

6.1.4. Part 2 – Repeat Dose, Morning Dose Administration, Days 14-17, Follow-up

	Day 14													Day 15	Day 16	Day 17	Follow Up (Day 20-22)	
	Pre-dose	0h	0.25h	0.5h	1h	1.5h	2h	4h	6h	8h	12h	18h	24h	36h	48h	72h		
Medical/medication/drug/alcohol history																	X	
Complete Physical Exam, Weight																X ¹	X	
Pregnancy Test ²																	X	
Fat Meal ³							X											
Triglyceride Assessment ³					X		←=====→											
Study Drug Dose ⁶		X ⁶																
Vital Signs (BP, HR, pulse)	X				X			X			X		X		X	X	X	
12-Lead ECG	X				X			X			X		X			X		
Hematology, Chemistry	X								X				X		X	X	X	
UA	X												X			X	X	
Exploratory PD Labs	X												X			X	X	
Plasma PK and Metabolite Sampling ^{3,4}	X		X	X	X	X	X	X	X	X	X	X	X	X	X	X		
Skin Biopsy ⁷					X ⁷				X ⁷				X ⁷					
Adverse Event Review	←=====→																	
BSFS ⁵	←=====→																	
Concomitant Medication Review	←=====→																	
Outpatient Visits																	X	
Inpatient Check-out																X		

1. Brief physical exam and weight Day 17 only
2. Serum hCG at follow up, all females.
3. Detailed Fat Meal, Triglyceride Assessment, Plasma PK Sampling and Plasma Metabolite Sampling can be found in Section 6.1.8.1
4. Plasma analysis for circulating metabolite profile; Plasma samples for metabolites will be analyzed from only the highest dose cohort.
5. The number of BSFS stool types will be collected in real time for each 24h period (Section 11.5).
6. For cohorts where multiple doses are to be administered either q1h or q16h, Time 0 is the first dose and subsequent doses are per regimen (q1h or q16) and the subsequent doses are not noted on the T&E Table.
7. Cohort 1 (10mg q16) collect only at 1h and 24h Day 14; Cohorts 2 & 3 (3mg, 1mg or 5mg q1h) collect only at 6h and 24h Day 14

6.1.5. Part 2 – Repeat Dose, Evening Dose Administration, Screening, Day -1, Day 1 and Day 2

	Screening (within 28d)	Day -1	Day 1 ⁽⁶⁾									Day 2 ⁽⁶⁾				
		PM	12h Pre-dose	Pre-dose	0h	0.25h	0.5h	1h	1.5h	2h	4h	6h	12h	14h	18h	24h
Informed Consent	X															
Medical/medication/drug/alcohol history	X	X														
Complete Physical Exam, Weight	X	X ¹														
HIV, Hep B, Hep C	X															
Pregnancy Test ²	X	X														
Estradiol/FSH ³	X															
Urine Drug, Cotinine & Alcohol Screen ⁴	X	X														
Fat Meal ⁵			X										X			
Triglyceride Assessment ⁵			←→										←=====→			
Study Drug Dose ⁶					X											
Vital Signs (BP, HR, pulse, Temp) ⁷	X	X	X	X			X			X						X
12-Lead ECG	X		X	X			X			X						X
Telemetry																
Hematology, Chemistry	X		X									X				X
UA	X		X													X
Exploratory PD Labs	X		X									X				
Plasma PK and Metabolite Sampling ^{5, 8}				X		X	X	X	X	X	X	X	X	X	X	X
Adverse Event Review			←=====→													
BSFS ⁹			←=====→													
Concomitant Medication Review			←=====→													
Outpatient Visits	X															
Inpatient Check-in		X														

- Brief physical exam, weight.
- Serum hCG at screening, urine hCG pre-dose on Day -1 – all females.
- If indicated
- An alcohol breath test is acceptable.
- Detailed Fat Meal, Triglyceride Assessment, Plasma PK Sampling and Plasma Metabolite Sampling can be found in Section 6.1.8.2

6. 0hr is relative to Study Dose administered and will be approximately at 18:00 hrs, making 12h Pre-dose approximately 06:00, 6h post-dose approximately 00:00 Day 2 and 12h post-dose approximately 06:00 Day 2. The actual nominal dose time will be the same for each subject within Part 2.
7. Temperature at Screening and Day -1 only.
8. The 24h time point is Day 2 pre-dose. Plasma analysis for circulating metabolite profile; Plasma samples for metabolites will be analyzed from only the highest dose cohort.
9. The number of BSFS stool types will be collected in real time for each 24h period (Section 11.5)

6.1.6. Part 2 – Repeat Dose, Evening Dose Administration, Days 3-13

	Days 3-13 ⁽¹⁾		
	12h Pre-dose	Pre-dose	0h
Study Drug Dose ¹			X
Vital Signs (BP, HR, pulse)		X ²	
12-Lead ECG		X ²	
Hematology, Chemistry		X ³	
UA		X ⁴	
Exploratory PD Labs	X ⁵		
Plasma PK and Metabolite Sampling		X ⁶	
Adverse Event Review	←=====→		
BSFS ⁸	←=====→		
Concomitant Medication Review	←=====→		

1. 0hr is relative to Study Dose administered and will be approximately at 18:00 hrs, making 12h Pre-dose approximately 06:00. The actual nominal dose time will be the same for each subject within Part 2.
2. Day 7, 12, and 13.
3. Day 4, and 7 only
4. Day 7 only
5. Day 7 12h Pre-dose only
6. Day 4, 5, 6, 12, and 13
7. The number of BSFS stool types will be collected each 24h period (Section 11.5)

6.1.7. Part 2 – Repeat Dose, Evening Dose Administration, Day 14-17, Follow-up

	Day 14								Day 15					Day 16		Day 17	Follow Up (Day 20-22)
	12h Pre- dose	0h	0.25h	0.5h	1h	1.5h	2h	4h	6h	12h	14h	18h	24h	36h	48h	72h	
Medical/medication/drug/alcohol history																	X
Complete Physical Exam, Weight																X ¹	X
Pregnancy Test ²																	X
Fat Meal ³	X																
Triglyceride Assessment ³	↔																
Study Drug Dose ⁴		X															
Vital Signs (BP, HR, pulse)	X				X			X		X			X	X			X
12-Lead ECG	X				X			X		X			X				
Hematology, Chemistry	X								X				X	X			X
UA	X													X			X
Exploratory PD Labs	X													X			X
Plasma PK and Metabolite Sampling ^{3,5}	X		X	X	X	X	X	X	X	X	X	X	X	X	X	X	
Adverse Event Review	←=====→																
BSFS ⁶	←=====→																
Concomitant Medication Review	←=====→																
Outpatient Visits																	X
Inpatient Check-out																X	

1. Brief physical exam and weight Day 17 only
2. Serum hCG at follow up, all females.
3. Detailed Fat Meal, Triglyceride Assessment, Plasma PK Sampling and Plasma Metabolite Sampling can be found in Section 6.1.8.2
4. 0hr is relative to Study Dose administered and will be approximately at 18:00 hrs, making 12h Pre-dose approximately 06:00 and 6h post-dose approximately 00:00 Day 15. The actual nominal dose time will be the same for each subject within Part 2.
5. Plasma analysis for circulating metabolite profile; Plasma samples for metabolites will be analyzed from only the highest dose cohort.
6. The number of BSFS stool types will be collected in real time for each 24h period (Section 11.5)

6.1.8. Part 2 – Repeat Dose, Fat Meal Challenge and Triglyceride Assessment Relative to Dose and PK Sampling

6.1.8.1. Morning Dose Administration, Day -1, Day 1, and Day 14

	Day -1, Day 1, Day 14															
	Pre-dose	0h	0.25h	0.5h	1h	1.5h	2h	3h	4h	5h	6h	7h	8h	9h	12h	18h
Study Drug Dose ¹		X														
Fat Meal							X									
Triglyceride Assessment					X		X	X	X	X	X	X	X	X	X	
Plasma Pharmacokinetic Sampling ^{1,2}	X		X	X	X	X	X		X		X		X		X	X

- Day 1 and 14 only. For cohorts where multiple doses are to be administered either q1h or q16h, Time 0 is the first dose and subsequent doses are per regimen (q1h or q16) and the subsequent doses are not noted on the T&E Table.
- PK Samples included in table to provide relative time to dosing, fat meal and triglyceride assessment. The full PK time points are found in Section 6.1.2, Section 6.1.3, and Section 6.1.4.

6.1.8.2. Evening Dose Administration, Day 1, Day 2, and Day 14

	Day 1, Day 2 and Day 14													
	Pre-dose (h)											0h	Post-dose (h)	
	11h	10h	9h	8h	7h	6h	5h	4h	3h	< 0.5h pre-dose	0.25h		0.5h	
Study Drug Dose ¹												X ^{1,3}		
Fat Meal		X												
Triglyceride Assessment	X	X	X	X	X	X	X	X	X	X	X			
Plasma Pharmacokinetic Sampling ²											X		X	X

- Day 1 and 14 only
- PK Samples included in table to provide relative time to dosing, fat meal and triglyceride assessment. The full PK time points are found in Section 6.1.5, Section 6.1.6, and Section 6.1.7.
- 0hr is relative to Study Dose administered and will be approximately at 18:00 hrs, making 12h Pre-dose approximately 06:00 and Making Day 2 Fat Meal 14h **Post**-Day 1 Dose (10h **Pre**-Day 2 Dose). The actual nominal dose time will be the same for each subject within Part 2.

6.1.9. Part 3 – Repeat Dose, Morning Dose Administration, Screening, Day -1, Day 1, Day 2

	Screening (within 28d)	Day -2, Day -1 ⁸	Day 1													Day 2	
			Pre-dose	0h	0.25h	0.5h	1h	1.5h	2h	4h	6h	8h	12h	18h	24h	0h	1h
Informed Consent	X																
Medical/medication/drug/alcohol history	X	X															
Complete Physical Exam, Weight	X	X ¹															
HIV, Hep B, Hep C	X																
Pregnancy Test ²	X	X															
Estradiol/FSH ³	X																
Urine Drug, Cotinine & Alcohol Screen ⁴	X	X															
Fat Meal ⁵		X							X								
Triglyceride Assessment ⁵		←→					X	←=====→									
Study Drug Dose				X													X
Vital Signs (BP, HR, pulse, Temp) ⁶	X	X	X				X			X			X		X	X	
12-Lead ECG	X		X				X			X			X		X		
Telemetry			←=====→														
Hematology, Chemistry	X	X										X				X	
UA	X	X														X	
Exploratory PD Labs	X		X													X	
Plasma PK Sampling ⁵			X		X	X	X	X	X	X	X	X	X	X	X		
Adverse Event Review			←=====→														
BSFS ⁷			←=====→														
Concomitant Medication Review			←=====→														
Outpatient Visits	X																
Inpatient Check-in		X															
Inpatient Check-out																	X

1. Brief physical exam, weight.
2. Serum hCG at screening and follow up, urine hCG pre-dose on Day -1 – all females.
3. If indicated.
4. An alcohol breath test is acceptable.

5. Detailed Fat Meal and Triglyceride Assessment relative to Dose and Plasma PK Sampling can be found in Section 6.1.15.1.
6. Temperature Screening and Day -1 only.
7. The number of BSFS stool types will be collected in real time for each 24h period (Section 11.5).
8. Based on logistics, check-in and all Day -1 assessments may occur on Day -2 with the exception of the Fat Meal and TG Assessment, both of which must be done on Day -1.

6.1.10. Part 3 – Repeat Dose, Morning Dose Administration, Days 7, 14, and 21*

	Days 7, 14, and 21	
	Pre-dose	0h
Medical/medication/drug/alcohol history	X	
Brief Physical Exam, Weight	X	
Study Drug Dose		X
Vital Signs (BP, HR, pulse)	X	
12-Lead ECG	X	
Hematology, Chemistry	X	
UA	X	
Exploratory PD Labs	X	
Plasma PK Sampling	X	
Adverse Event Review	←=====→	
BSFS ¹	←=====→	
Concomitant Medication Review	←=====→	
Outpatient Visits	X	

1. The number of BSFS stool types will be collected in real time for each 24h period while at home (Section 11.5). BSFS Diary Cards to be brought to the unit and reviewed/data entered during the visit.

*NOTE for Days 3-6, 8-13, 15-20, and 22-27: Subjects will dose at home and maintain BSFS Diary cards as directed.

6.1.11. Part 3 – Repeat Dose, Morning Dose Administration, Day 27-31 and Follow-up

	Day 27	Day 28														Day 29	Day 30	Day 31	Follow Up (Day 34-36)			
	PM	Pre-dose	0h	0.25h	0.5h	1h	1.5h	2h	4h	6h	8h	12h	18h	24h	36h	48h	72h					
Medical/medication/drug/alcohol history	X																	X				
Complete Physical Exam, Weight	X ¹																X ¹	X				
Pregnancy Test ²																		X				
Fat Meal ³								X	←-----→													
Triglyceride Assessment ³						X	←-----→															
Study Drug Dose			X																			
Vital Signs (BP, HR, pulse)	X	X				X			X			X		X		X	X	X	X			
12-Lead ECG		X				X			X			X		X		X		X				
Hematology, Chemistry		X								X				X		X	X	X				
UA		X												X			X	X				
Exploratory PD Labs		X												X			X	X				
Plasma PK Sampling ³		X		X	X	X	X	X	X	X	X	X	X	X	X	X	X					
Adverse Event Review	←-----→																					
BSFS ⁴	←-----→																					
Concomitant Medication Review	←-----→																					
Outpatient Visits																			X			
Inpatient Check-in	X																					
Inpatient Check-out																		X				

1. Brief physical exam and weight Day 27 and 31
2. Serum hCG at follow up, all females.
3. Detailed Fat Meal, Triglyceride Assessment and Plasma PK Sampling can be found in Section 6.1.15.1
4. The number of BSFS stool types will be collected in real time for each 24h period (Section 11.5). BSFS Diary Cards to be bought to the unit and reviewed/data entered during the visit.

6.1.12. Part 3 – Repeat Dose, Evening Dose Administration, Screening, Day 1 and Day 2

	Screening (within 28d)	Day -1	Day 1 ⁽⁶⁾										Day 2 ⁽⁶⁾					
		PM	12h Pre-dose	Pre-dose	0h	0.25h	0.5h	1h	1.5h	2h	4h	6h	12h	14h	18h	24h	0h	1h
Informed Consent	X																	
Medical/medication/drug/alcohol history	X	X																
Complete Physical Exam, Weight	X	X ¹																
HIV, Hep B, Hep C	X																	
Pregnancy Test ²	X	X																
Estradiol/FSH ³	X																	
Urine Drug, Cotinine & Alcohol Screen ⁴	X	X																
Fat Meal ⁵			X										X					
Triglyceride Assessment ⁵			←→										←=====→					
Study Drug Dose ⁶					X												X	
Vital Signs (BP, HR, pulse, Temp) ⁷	X	X	X	X				X				X						
12-Lead ECG	X		X	X				X				X						
Telemetry					←=====→													
Hematology, Chemistry	X		X									X					X	
UA	X		X														X	
Exploratory PD Labs	X		X										X					
Plasma PK Sampling ^{5, 8}				X		X	X	X	X	X	X	X	X	X	X			
Adverse Event Review			←=====→															
BSFS ⁹			←=====→															
Concomitant Medication Review			←=====→															
Outpatient Visits	X																	
Inpatient Check-in		X																
Inpatient Check-out																		X

1. Brief physical exam, weight.
2. Serum hCG at screening, urine hCG pre-dose on Day -1 – all females.
3. If indicated
4. An alcohol breath test is acceptable.

5. Detailed Fat Meal, Triglyceride Assessment, Plasma PK Sampling and Plasma Sampling can be found in Section 6.1.15.2
6. 0hr is relative to Study Dose administered and will be approximately at 18:00 hrs, making 12h Pre-dose approximately 06:00, 6h post-dose approximately 00:00 Day 2 and 12h post-dose approximately 06:00 Day 2. The actual nominal dose time will be the same for each subject within Part 3.
7. Temperature at Screening and Day -1 only.
8. The 24h time point is Day 2 pre-dose.
9. The number of BSFS stool types will be collected in real time for each 24h period (Section 11.5)

6.1.13. Part 3 – Repeat Dose, Evening Dose Administration, Days 7, 14, and 21*

	Days 7, 14, and 21 ⁽²⁾	
	Pre-dose	0h
Medical/medication/drug/alcohol history	X	
Brief Physical Exam, Weight	X	
Study Drug Dose		X
Vital Signs (BP, HR, pulse)	X	
12-Lead ECG	X	
Hematology, Chemistry	X	
UA	X	
Exploratory PD Labs	X	
Plasma PK Sampling	X	
Adverse Event Review	← ===== →	
BSFS ¹	← ===== →	
Concomitant Medication Review	← ===== →	
Outpatient Visits	X	

1. The number of BSFS stool types will be collected in real time for each 24h period while at home (Section 11.5). BSFS Diary Cards to be bought to the unit and reviewed/data entered during the visit.
2. 0hr is relative to Study Dose administered and will be approximately at 18:00 hrs. The actual nominal dose time will be the same for each subject within Part 3.

*NOTE for Days 3-6, 8-13, 15-20, and 22-27: Subjects will dose at home and maintain BSFS Diary cards as directed. If subjects are checking into the unit prior to dosing on Day 27, the dose may be administered in the unit rather than at home

6.1.14. Part 3 – Repeat Dose, Evening Dose Administration, Day 27-31 and Follow-up

	Day 27	Day 28								Day 29					Day 30		Day 31	Follow Up (Day 34-36)
	PM	12h Pre- dose	0h	0.25h	0.5h	1h	1.5h	2h	4h	6h	12h	14h	18h	24h	36h	48h	72h	
Medical/medication/drug/alcohol history	X																	X
Complete Physical Exam, Weight	X ¹																X ¹	X
Pregnancy Test ²																		X
Fat Meal ³	X	X																
Triglyceride Assessment ³		←→																
Study Drug Dose ⁴	X		X															
Vital Signs (BP, HR, pulse)	X	X				X			X		X			X	X			X
12-Lead ECG		X				X			X		X			X				
Hematology, Chemistry		X								X				X	X			X
UA		X													X			X
Exploratory PD Labs		X													X			X
Plasma PK Sampling ³		X		X	X	X	X	X	X	X	X	X	X	X	X	X	X	
Adverse Event Review		←=====→																
BSFS ⁵		←=====→																
Concomitant Medication Review		←=====→																
Outpatient Visits																		X
Inpatient Check-out	X																	
Inpatient Check-out																	X	

1. Brief physical exam and weight Day 17 only
2. Serum hCG at follow up, all females.
3. Detailed Fat Meal, Triglyceride Assessment and Plasma PK Sampling can be found in Section [6.1.15.2](#)
4. 0hr is relative to Study Dose administered and will be approximately at 18:00 hrs, making 12h Pre-dose approximately 06:00 and 6h post-dose approximately 00:00 Day 29. Day 27 dose may be administered in the unit rather than at home if the subject has checked in prior to Day 27 dose. The actual nominal dose time will be the same for each subject within Part 3.
5. The number of BSFS stool types will be collected in real time for each 24h period (Section [11.5](#)). BSFS Diary Cards to be bought to the unit and reviewed/data entered during the visit.

6.1.15. Part 3 – Repeat Dose, Fat Meal Challenge and Triglyceride Assessment Relative to Dose and PK Sampling

6.1.15.1. Morning Dose Administration, Day -1, Day 1, and Day 28

	Day -1, Day 1, Day 28															
	Pre-dose	0h	0.25h	0.5h	1h	1.5h	2h	3h	4h	5h	6h	7h	8h	9h	12h	18h
Study Drug Dose ¹		X														
Fat Meal							X									
Triglyceride Assessment					X		X	X	X	X	X	X	X	X	X	
Plasma Pharmacokinetic Sampling ^{1,2}	X		X	X	X	X	X		X		X		X		X	X

- Day 1 and 28 only
- PK Samples included in table to provide relative time to dosing, fat meal and triglyceride assessment. The full PK time points are found in Section 6.1.9, Section 6.1.10, and Section 6.1.11.

6.1.15.2. Evening Dose Administration, Day 1, Day 2, and Day 28

	Day 1, Day 2 and Day 28													
	Pre-dose (h)											0h	Post-dose (h)	
	11h	10h	9h	8h	7h	6h	5h	4h	3h	< 0.5h pre-dose	0.25h		0.5h	
Study Drug Dose ¹												X ³		
Fat Meal		X												
Triglyceride Assessment	X	X	X	X	X	X	X	X	X		X			
Plasma Pharmacokinetic Sampling ^{1,2}											X		X	X

- Day 1, Day 2, and 28 only
- PK Samples included in table to provide relative time to dosing, fat meal and triglyceride assessment. The full PK time points are found in Section 6.1.12, Section 6.1.13, and Section 6.1.14.
- 0hr is relative to Study Dose administered and will be approximately at 18:00 hrs, making 12h Pre-dose approximately 06:00 and Making Day 2 Fat Meal 14h **Post**-Day 1 Dose (10h **Pre**-Day 2 Dose). The actual nominal dose time will be the same for each subject within Part 3.

6.2. Screening and Critical Baseline Assessments

Cardiovascular medical history/risk factors (as detailed in the CRF) will be assessed at screening.

The following demographic parameters will be captured: year of birth, sex, race and ethnicity.

Medical/medication/family history will be assessed at screening as related to the inclusion/exclusion criteria listed in Section 4. All subsequent assessments will be updates.

6.3. Safety

Planned time points for all safety assessments are listed in the Time and Events Table (Section 6.1). Additional time points for safety tests (such as vital signs, physical exams and laboratory safety tests) may be added during the course of the study based on newly available data to ensure appropriate safety monitoring.

6.3.1. Adverse Events (AE) and Serious Adverse Events (SAEs)

The definitions of an AE or SAE can be found in [Appendix 3](#) (Section 11.3)

The investigator and their designees are responsible for detecting, documenting and reporting events that meet the definition of an AE or SAE.

6.3.1.1. Time period and Frequency for collecting AE and SAE information

- Any SAEs assessed as related to study participation (e.g., protocol-mandated procedures, invasive tests, or change in existing therapy) or related to a GSK product will be recorded from the time a subject consents to participate in the study up to and including any follow-up contact.
- AEs will be collected from the start of Study Treatment until the follow-up contact (see Section 6.3.1.3), at the time points specified in the Time and Events Table (Section 6.1).
- Medical occurrences that begin prior to the start of study treatment but after obtaining informed consent may be recorded on the Medical History/Current Medical Conditions section of the CRF.
- All SAEs will be recorded and reported to GSK within 24 hours, as indicated in Section 11.3.
- Investigators are not obligated to actively seek AEs or SAEs in former study subjects. However, if the investigator learns of any SAE, including a death, at any time after a subject has been discharged from the study, and he/she considers the event reasonably related to the study treatment or study participation, the investigator must promptly notify GSK.

NOTE: The method of recording, evaluating and assessing causality of AEs and SAEs plus procedures for completing and transmitting SAE reports to GSK are provided in Section 11.3.

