8.2. Sample Size Considerations

Sample sizes are based on feasibility. No formal power calculations were performed.

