#### 7.1.1.1. Adverse Events

Adverse events will be assessed for Part 1 and Part 2 separately. Adverse events will be summarized by the cohort of active treatments and pooling of placebo subjects within each part.

An AE is any untoward medical occurrence in a patient or clinical investigation subject, temporally associated with the use of a medicinal product, whether or not considered related to the medicinal product.

No distinction will be made between pre-treatment AEs and treatment emergent AEs in this study, as AE collection is scheduled to start after first dose of study medication.

AE verbatim text will be coded and classified by system organ class (SOC) (body system) and preferred term (PT) using MedDRA (current version 19.0).

AEs will be summarized by number of subjects and percentage of total subjects, by SOC and PT. Summaries and listings will be provided for all AEs, AEs by severity, drug-related AEs, serious AEs, and AEs leading to drug withdrawal.

The details can be found at [Appendix 12](#): List of Data Displays as well as at the file of the mock shell.

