#### 11.4.2.1. Treatment States for AE Data

Treatment State	Definition
Pre-Treatment	AE Start Date < Study Treatment Start Date
On-Treatment	If AE onset date is on or after treatment start date & on or before treatment stop date. Study Treatment Start Date $\leq$ AE Start Date $\leq$ Study Treatment Stop Date
Post-Treatment	If AE onset date is after the treatment stop date. AE Start Date > Study Treatment Stop Date
Onset Time Since 1 st Dose (Days)	If Treatment Start Date > AE Onset Date = AE Onset Date - Treatment Start Date If Treatment Start Date $\leq$ AE Onset Date = AE Onset Date - Treatment Start Date + 1 Missing otherwise.
Duration (Days)	AE Resolution Date – AE Onset Date + 1
Drug-related	If relationship is marked 'YES' on eCRF.

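### The SAP waives any pre-dose/post-dose split of adverse events on a premise that is false for participation- or product-related SAEs, which are recorded from consent

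*Protocol*

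**What the plan says.** Protocol 6.3.1.1 sets two different starting points.

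- "Any SAEs assessed as related to study participation", or to a GSK product, "will be recorded from the time a subject consents to participate in the study up to and including any follow-up contact". Protocol-mandated procedures and invasive tests are among its examples of participation.
- For adverse events in general, "AEs will be collected from the start of Study Treatment until the follow-up contact". Events before dosing that fall outside the SAE rule have another destination: "Medical occurrences that begin prior to the start of study treatment but after obtaining informed consent may be recorded on the" medical history page of the CRF.

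SAP 7.1.1.1 recognises only the second starting point: "No distinction will be made between pre-treatment AEs and treatment emergent AEs in this study, as AE collection is scheduled to start after first dose". It summarises events by active cohort, with placebo pooled within each part. SAP 7.1.1.5 has SAEs summarised by the same method as all AEs.

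SAP 11.4.2.1 nevertheless defines three states for AE data. The Pre-Treatment state is "AE Start Date < Study Treatment Start Date". The same table gives an onset-day formula for events that begin before treatment.

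In SAP Appendix 12, Tables 3.1–3.4 (all AEs and GI AEs) and 3.9–3.10 (SAEs) use the Safety population. None of them states an on-treatment restriction or refers to the Appendix 4 states.

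**The concern.** The SAP's reason for not separating pre-dose events does not hold for one class of event that the protocol deliberately collects before dosing. Subjects undergo study procedures in that period: screening within 28 days of dosing, then a Day -1 fat meal with serial triglyceride sampling. A related SAE during that time is what the consent-onward rule exists to capture.

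Safety and tolerability are the primary endpoint in both parts, and each planned active column holds six subjects. An SAE that preceded any drug, but was printed in a dose column, would be read as an event on that dose. The SAP also leaves a programmer with two unreconciled texts: an analysis section that waives the distinction and an appendix that defines it.

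**Working it through.** There is no sample-size, power or alpha figure to reproduce; Protocol 8.2 states "Sample sizes are based on feasibility. No formal power calculations were performed". The check is a comparison of the sections, followed by simple division.

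**Step 1. Which events can be in the data before the first dose?** By Protocol 6.3.1.1, SAEs related to participation or to a GSK product. Other pre-dose occurrences may go to medical history, and non-serious AEs are not collected until treatment starts. The SAP premise is therefore right for AEs generally and wrong for this SAE subset.

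**Step 2. Which of those subjects can reach a table?** SAP Section 4 defines the Safety population as subjects with at least one dose of study medication. A pre-dose SAE in a subject who is never dosed stays out of the regimen columns. One in a subject who is later dosed qualifies.

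**Step 3. Does anything remove the event?** SAP 7.1.1.1 waives the distinction, 7.1.1.5 treats SAEs in the same way, and the table list carries no restriction. Taken together, these place the event under the subject's regimen or pooled placebo. This is the combined effect of three sections; no single sentence states it as a rule.

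**Step 4. Would the existing states settle it?** Not fully.

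- Day 1: SAP 11.4.2.1 works on dates, and an event dated on the treatment start date is On-Treatment even if it began before the dose. SAP 11.4.1, for phases, puts a date equal to the treatment start date in Pre-Treatment. The two definitions disagree on Day 1.
- Missing start day: SAP 11.7.2.1 uses the first of the month, or the treatment start date if the first falls earlier, and then calls the event on-treatment.
- Completely missing start date: SAP 11.7.2.1 leaves it missing.

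**Step 5. Size of one misplaced event.** Allocation is 6 active to 2 placebo per cohort in Parts 1 and 2 (Protocol 3.2). Part 1 had 11 cohorts, with Cohort 9 cancelled (SAP 11.5.1), leaving 10. Part 2 had 3.

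| Column | Planned n | Effect of one event |
|---|---|---|
| Active cohort, either part | 6 | 0/6 becomes 1/6 = 16.7% |
| Part 2 pooled placebo | 3 × 2 = 6 | adds 1/6 = 16.7% |
| Part 1 pooled placebo | 10 × 2 = 20 | adds 1/20 = 5.0% |

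These figures show the effect of a single event. They say nothing about how likely one is.

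**The case against.** The case for leaving the text alone has real substance.

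- **The premise is right for most events.** A reader might infer that all SAEs are collected from consent. Protocol 6.3.1.1 does not say that: the early window covers only SAEs judged related to participation or to a GSK product.
- **The SAP does contain the distinction.** A reader might infer that the SAP as a whole draws no line at first dose, or that 7.1.1.1 sets the Appendix 4 states aside. Neither is supported. Section 7.1.1.1 never mentions those states, Appendix 4 remains among the data-handling rules in SAP Section 5, and on-treatment status is used in the partial-date rules.
- **Few subjects could be affected.** The subject must have a related SAE, still be judged eligible, and then be dosed.
- **The event would be traceable.** SAEs are listed individually (Listings 15 and 16), and onset relative to first dose is derived.
- **Calendar time is not risk.** With 28 days of screening, pre-dose time could be 28/(28+8) = 78% to 28/(28+6) = 82% of the SAE window in Part 1, and 28/(28+22) = 56% to 28/(28+20) = 58% in Part 2. It is tempting to read these as exposure to the problem. They use the maximum screening length, and only related events count, so they do not measure probability.
- **A blunt filter could do harm.** Restricting every table to events with onset at or after first dose could drop events whose start date is missing. Neither document shows that AE onset time is captured, which limits what can be done on Day 1.

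All of this stands. It limits the likelihood and breadth of the problem and shapes the remedy. It does not make the 7.1.1.1 premise true, and it does not supply a rule that keeps a known pre-dose SAE out of the tables.

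**Conclusion.** The point holds in a narrow form and is minor. The premise of SAP 7.1.1.1 conflicts with Protocol 6.3.1.1 for participation- or product-related SAEs, and the waiver built on it conflicts with SAP 11.4.2.1. Followed as written, the AE and SAE tables would attribute a related pre-dose SAE, in a later-dosed subject, to that subject's regimen. The sizes in the working assume the planned column counts.

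The conclusion also assumes that the tables are programmed from 7.1.1.1 and Appendix 12 as they stand, without an unstated filter. The documents report no such SAE and give no expected rate; in subjects healthy enough to be dosed, such events should be rare. The documents do not support a claim that any table is in fact wrong, only that the stated rules would produce a wrong entry if such an event occurred.

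**What to change.** In SAP 7.1.1.1, replace the sentence that waives the distinction with text to this effect:

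1. SAEs related to study participation or to a GSK product are collected from consent; other AEs are collected from the start of study treatment.
2. The AE and SAE summary tables exclude only events known to have started before the first dose: those in the Pre-Treatment state of 11.4.2.1, plus Day 1 events recorded as pre-dose where an onset time is available.
3. Events with a missing or ambiguous onset stay in the tables.
4. Pre-dose SAEs appear in a separate listing, flagged as such.

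Add a cross-reference to 11.4.2.1 and align the Day 1 rule there with 11.4.1.

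The cost is a small redefinition of the state flag for Day 1, one extra listing and a short text change. Where onset time was not collected, a Day 1 event with unclear timing simply remains in the tables, so real on-treatment events are not lost. The change is best made before the randomisation codes are released.
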